5.5.2 Storage, re-use and destruction of pharmacogenetic samples

The processes adopted for the coding and storage of samples for genetic analysis are important to maintain subject confidentiality. Samples will be stored for a maximum of 15 years from the date of the Last Subject's Last Visit, after which they will be destroyed. DNA is a finite resource that may be used up during analyses. The results of any further analyses will be reported either in the Clinical Study Report itself or as an addendum, or separately in a scientific report or publication. Samples will be stored and used until no further analyses are possible or the maximum storage time has been reached.

Refer to [Appendix G](#) for details of the optional (DNA) genetic research.

5.6 Exploratory Research

If a patient agrees to participate in the exploratory biomarker research component of the study, biological samples (eg, plasma, serum, archived and study-obtained tumour, etc) will be collected and may be analysed for exploratory biomarkers to assess correlations with disease activity, effects of study drug and clinical outcomes.

The results of this exploratory biomarker research will be reported separately and will not form part of the Clinical Study Report.

The results of this exploratory biomarker research may be pooled with biomarker data from other studies with the study drug to generate hypotheses to be tested in future studies.

5.6.1 Collection of tumour biopsy samples

5.6.1.1 Archival tumour

All patients eligible for the study will be asked to supply a sample of their archival tumour, if a sample taken at the time of diagnosis is available (blocks preferred, slides acceptable). Any archival biopsy samples taken following previous lines of therapy are also requested, if available. In each case the prior treatment must be clearly indicated for each sample provided. This sample will be used to support exploratory biomarker analyses (see Section 5.6.3.1)

5.6.1.2 Optional tissue collection at screening

Patients will be asked to consent to provide additional tumour tissue at screening, which can be collected at the same time as the mandatory screening tumour biopsy (see Section 4.1), where appropriate to do so. This biopsy will be used to support the development of the diagnostic test for approval by CFDA (China) and/or for exploratory biomarker analyses (see Section 5.6.3.1).

5.6.1.3 Discontinuation Biopsy

Patients will also be asked to consent to a further optional biopsy, to be collected at discontinuation of investigational product. This sample will be used to support exploratory biomarker analyses (see Section 5.6.3).

For timings of all tumour biopsy samples requested see Table 4 below.

Table 4 Tumour biopsy samples

Time relative to dose	Requirement
Archival	M*
Screening	M+O
Discontinuation or progression ¹	O

¹ To be taken at discontinuation or progression, whichever occurs first.

M=Mandatory **O=Optional** **M*=mandatory if available**

Tumour samples should be provided in the form of a formalin fixed paraffin embedded block (tissue derived from the diagnostic tumour or a metastatic site). If this is not possible, the following may be provided:

- 10-20 slides of freshly prepared unstained 5-micron sections from the mandatory screening FFPE tumour block may be provided (minimum 10 slides is required)
- 10-20 slides of freshly prepared unstained 5-micron sections from the archival tumour block may be provided.

Further details on sample processing, handling and shipment are provided in the Laboratory Manual.

5.6.2 Collection of plasma for exploratory analyses

All patients will be required to provide a series of plasma samples. The Screening Visit sample is to be taken at the same time as the screening biopsy is taken or prior to T790M mutation analysis. All plasma samples from screening visit are required by AstraZeneca, regardless of the T790M mutation results. All samples from Visit 2 onward are to be drawn pre-dose as described in the Study Plan ([Table 1](#), [Table 2](#) and [Table 5](#)) below. These samples will be used primarily, but not exclusively, for the extraction and analysis of circulating tumour DNA (ctDNA). The ctDNA samples will be used to further explore EGFR (and other gene) mutation status and may be used to develop a plasma-based diagnostic test. Plasma samples collected on the trial may also be used (in an exploratory fashion) as a pharmacodynamics measure of drug activity.

Table 5 Plasma for exploratory analyses²

Visit (sample taken pre dose)	ctDNA collection
Screening	X
Cycle 1 Day 1	X
Cycle 1 Day 8	X
Cycle 1 Day 15	X
Cycle 2 Day 1	X
Cycle 3 Day 1	X
Cycle 4 Day 1	X
Cycle 5 Day 1	X
Cycle 6 Day 1	X
Cycle 7 Day 1 (and every 6 week onwards) ¹	X

Table 5 Plasma for exploratory analyses²

Visit (sample taken pre dose)	ctDNA collection
Treatment Discontinuation	X
Progression Follow-up (every 6 weeks) ²	X
Time of Progression ¹	X

¹ Plasma for ctDNA are only collected according to above schedule prior to RECIST modules freeze time (24 months post LSFD), after RECIST modules freeze time, ctDNA plasma will be collected every 12 weeks up to and including progression, until final DCO.

² For patients who discontinue treatment prior to progression.

Details on sample processing, handling, shipment and storage are provided in the Laboratory Manual.

5.6.3 Exploratory Analyses

5.6.3.1 Exploratory Biomarker Analyses

Biological samples (eg, plasma, serum, archived and study-obtained tumour, etc) will be collected and may be analysed for exploratory research into factors that may influence susceptibility to/development of NSCLC/cancer and/or response to AZD9291.

The biomarkers to be investigated using tumour samples collected will not necessarily be limited to but will include all or some of the following:

- EGFR
- MET
- HER2
- MAPK
- AKT
- PDL-1

5.6.3.2 Exploratory analyses to support companion diagnostic development

The mutation test being used to select T790M mutation positive patients for this study is being developed for approval as a companion diagnostic for AZD9291. An optional second screening tissue sample (see Section 5.6.1.2), and some residual tissue from the mandatory screening biopsy may be used to support the diagnostic development of this assay.

ctDNA samples collected during the study may be used to develop a plasma-based diagnostic test.

5.7 Management of Biological Samples

5.7.1 Storage, re-use and destruction of biological samples

Samples will be stored for a maximum of 15 years from the date of the Last Subject's Last Visit, after which they will be destroyed. The results of this biomarker research will be reported either in the Clinical Study Report itself or as an addendum, or separately in a scientific report or publication. The results of this biomarker research may be pooled with biomarker data from other studies with the study drug to generate hypotheses to be tested in future research.

5.7.2 Labelling and shipment of biological samples

The Principal Investigator ensures that samples are labelled and shipped in accordance with the Laboratory Manual and the Biological Substance, Category B Regulations (materials containing or suspected to contain infectious substances that do not meet Category A criteria), see [Appendix B](#)'IATA 6.2 Guidance Document'.

Any samples identified as Infectious Category A materials are not shipped and no further samples will be taken from the subject unless agreed with AstraZeneca and appropriate labelling, shipment and containment provisions are approved.

All tumour samples should be shipped at ambient temperature as per the Laboratory Manual to the AstraZeneca designated central Contract Research Organisation.

5.7.3 Chain of custody of biological samples

A full chain of custody is maintained for all samples throughout their lifecycle.

The Principal Investigator at each centre keeps full traceability of collected biological samples from the subjects while in storage at the centre until shipment or disposal (where appropriate) and keeps documentation of receipt of arrival.

The sample receiver keeps full traceability of the samples while in storage and during use until used or disposed of or until further shipment and keeps documentation of receipt of arrival.

AstraZeneca keeps oversight of the entire life cycle through internal procedures, monitoring of study sites and auditing of external laboratory providers.

Samples retained for further use are registered in the AstraZeneca Biobank during the entire life cycle.

5.7.4 Withdrawal of informed consent for donated biological samples

If a subject withdraws consent to the use of donated biological samples, the samples will be disposed of/destroyed, and the action documented. If samples are already analysed, AstraZeneca is not obliged to destroy the results of this research.

The Principal Investigator:

- Ensures subjects' withdrawal of informed consent to the use of donated samples is notified immediately to AstraZeneca
- Ensures that biological samples from that subject, if stored at the study site, are immediately identified, disposed of /destroyed, and the action documented
- Ensures the laboratory (ies) holding the samples is/are informed about the withdrawn consent immediately and that samples are disposed of/destroyed, the action documented and the signed document returned to the study site
- Ensures that the subject and AstraZeneca are informed about the sample disposal.

AstraZeneca ensures the central laboratory (ies) holding the samples is/are informed about the withdrawn consent immediately and that samples are disposed of/destroyed and the action documented and returned to the study site.

AstraZeneca ensures that biological samples are destroyed at the end of a specified period as described in the informed consent.

5.8 Post progression outcomes

The date of second progression up to RECIST modules freeze time (24 months post LSFD) will be recorded by an investigator and defined according to local standard clinical practice and may involve any of; objective radiological or symptomatic progression or death. Second progression status up to RECIST modules freeze time (24 months post LSFD) will be reviewed every 6 weeks following the progression event used for the primary variable PFS (the first progression) and status recorded. To support PFS2, the time to start of subsequent treatment will be recorded up to RECIST modules freeze time.

6. SAFETY REPORTING AND MEDICAL MANAGEMENT

The Principal Investigator is responsible for ensuring that all staff involved in the study are familiar with the content of this section.

6.1 Definition of adverse events

An adverse event is the development of an undesirable medical condition or the deterioration of a pre-existing medical condition following or during exposure to a pharmaceutical product, whether or not considered causally related to the product. An undesirable medical condition can be symptoms (eg, nausea, chest pain), signs (eg, tachycardia, enlarged liver) or the abnormal results of an investigation (eg, laboratory findings, electrocardiogram). In clinical studies, an AE can include an undesirable medical condition occurring at any time, including run-in or washout periods, even if no study treatment has been administered.

The term AE is used to include both serious and non-serious AEs.

For cases where it could be suspected that a tissue-derived medicine has been contaminated by a pathogen, information about any of the above conditions (including infection) should be collected. Any deterioration of the disease targeted in the study and associated symptoms should not be regarded as an adverse event.

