6.3.8 Disease progression

Disease progression can be considered as a worsening of a subject's condition attributable to the disease for which the investigational product is being studied. It may be an increase in the severity of the disease under study and/or increases in the symptoms of the disease. The development of new, or progression of existing metastasis to the primary cancer under study should be considered as disease progression and not an AE. Events, which are unequivocally due to disease progression, should not be reported as an AE during the study.

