6.3.9 New cancers

The development of a new cancer should be regarded as an AE and will generally meet at least one of the serious criteria. New cancers are those that are not the primary reason for the administration of the study treatment and have been identified after the patient's inclusion in this study. They do not include metastases of the original cancer.

Progression of the malignancy under study, including signs and symptoms progression, should not be reported as a serious adverse event. Hospitalization due to signs and symptoms of disease progression should not be reported as serious adverse event.

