6.3.10 Handling of deaths

All deaths that occur during the study, or within the follow-up period after the administration of the last dose of investigational product, should be reported as follows:

- Death, which is unequivocally due to disease progression, should be communicated to the study monitor at the next monitoring visit and should be documented in the CRF module, but should not be reported as a SAE during the study
- Where death is not clearly due to disease progression of the disease under study the AE causing the death should be reported to the study monitor as an SAE within 24 hours. The report should contain a comment regarding the co-involvement of progression of disease, if appropriate, and should assign a single primary cause of death together with any contributory causes
- Deaths with an unknown cause should always be reported as a SAE but every effort should be made to establish a cause of death. A post-mortem may be helpful in the assessment of the cause of death, and if performed a copy of the post-mortem results (with translation of important parts into English) should be reported in an expedited fashion to an AstraZeneca representative within the usual timeframes

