6.7 Management of Investigational Product related toxicities

If a patient experiences a CTCAE grade 3 or higher and/or unacceptable toxicity (any grade) not attributable to the disease or disease-related processes under investigation, where the Investigator considers the AE of concern to be specifically associated with AZD9291, dosing will be interrupted and supportive therapy administered as required in accordance with local practice/guidelines.

If the toxicity resolves or reverts to \leq CTCAE grade 2 within 3 weeks of onset, treatment with AZD9291 may be restarted at the same dose (80 mg) or a lower dose (40 mg) using the rules below for dose modifications (Table 7) and with discussion and agreement with the AstraZeneca Study Physician as needed. There will be no individual modifications to dosing schedule in response to toxicity, only potential dose reduction or dose interruption.

If the toxicity does not resolve to \leq CTCAE grade 2 after 3 weeks, then the patient should permanently discontinue the study treatment and be observed until resolution of the toxicity.

Table 7 Dose interventions

Intervention	AZD9291 Dose
Starting Dose	80 mg
Reduced Dose -1	40 mg

On resolution of toxicity within 3 weeks:

- If an AE subsequently requires dose interruption, AZD9291 may restart at the same dose or the reduced dose, on resolution/improvement of the AE at the discretion of the Investigator.

If new or worsening pulmonary symptoms (eg, dyspnoea) or radiological abnormality suggestive of interstitial lung disease is observed, an interruption in study treatment dosing is recommended, and the AstraZeneca study physician should be informed. A questionnaire regarding the results of the full diagnostic workup (including high-resolution computed tomography (HRCT), blood and sputum culture, haematological parameters) will be sent to Investigators. It is strongly recommended to perform a full diagnostic workup, to exclude alternative causes such as lymphangitic carcinomatosis, infection, allergy, cardiogenic edema, or pulmonary hemorrhage. In the presence of confirmatory HRCT scans where other causes of respiratory symptoms have been excluded, a diagnosis of interstitial lung disease should be considered and study treatment permanently discontinued.

In the absence of a diagnosis of interstitial lung disease study treatment may be restarted following consultation with the AstraZeneca Study Physician.

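### Sections 6.1 and 6.3.9 exclude progression symptoms and admissions from AE/SAE reporting without the certainty qualifier used in 6.3.6, 6.3.8 and 6.3.10

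*Protocol*

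**What the plan says.** Two sections exclude disease-related events with no statement of how sure the investigator must be.

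- Section 6.1, in the AE definition: "Any deterioration of the disease targeted in the study and associated symptoms should not be regarded as an adverse event".
- Section 6.3.9, under the heading on new cancers: "Progression of the malignancy under study, including signs and symptoms progression, should not be reported as a serious adverse event". It continues: "Hospitalization due to signs and symptoms of disease progression should not be reported as serious adverse event".

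Three sections exclude only what is certain.

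- Section 6.3.8: "Events, which are unequivocally due to disease progression, should not be reported as an AE during the study".
- Section 6.3.10: "Death, which is unequivocally due to disease progression, should be communicated to the study monitor at the next monitoring visit" and is not reported as an SAE. The opposite case, introduced by "Where death is not clearly due to disease progression of the disease under study", must be reported as an SAE within 24 hours.
- Section 6.3.6 applies the unequivocal standard to laboratory values.

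Section 6.7 separately covers lung events. It begins "If new or worsening pulmonary symptoms (eg, dyspnoea) or radiological abnormality suggestive of interstitial lung disease is observed" and provides for informing the sponsor's study physician, a questionnaire and a strongly recommended diagnostic work-up.

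**The concern.** The same document gives sites two rules for the same decision. The difference matters for events that could be either tumour or drug. In lung cancer these are common presentations: Sections 5.3.2.1 and 8.4 list dyspnoea, cough and chest pain among the lung cancer symptoms, while Section 6.7 treats new or worsening dyspnoea as a possible sign of interstitial lung disease. Patients may also stay on AZD9291 after progression (Sections 1.5 and 4.2), so drug exposure and progression symptoms can coexist by design.

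Safety and tolerability are a secondary objective (Section 2.2). There is no control arm in which the same reporting habits would apply, and no data monitoring committee is planned (Section 6.8.1). AE and SAE rates will be read at face value, so a rate that depends on which section a site followed is hard to interpret.

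**Working it through.** The protocol states no figure on this point, so the check is a comparison of texts, followed by one simple scale calculation.

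**Step 1. The rules side by side**

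| Section | What it governs | Certainty needed to leave an event out |
|---|---|---|
| 6.1 | AE definition | None stated |
| 6.3.9 | SAE reporting of progression and of admissions due to it | None stated |
| 6.3.6 | Laboratory values | Unequivocal |
| 6.3.8 | AE reporting of progression | Unequivocal |
| 6.3.10 | Deaths | Unequivocal; a death not clearly due to progression is an SAE |

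Two sections have no threshold and three have one.

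**Step 2. Does the stricter rule clearly prevail?** It does not.

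- Section 6.2 defines an SAE as an AE that meets a seriousness criterion. Whatever 6.1 removes from the AE definition cannot become an SAE, so the duty in 6.4 to report every SAE regardless of causality is never reached.
- The reporting sentence in 6.3.8 speaks of AEs. For SAEs and hospitalisations, 6.3.9 is the more specific text, and it has no qualifier.
- Section 6.3.8 describes progression broadly: "It may be an increase in the severity of the disease under study and/or increases in the symptoms of the disease". No imaging is required, so worsening symptoms alone can be called progression and then fall under 6.3.9.

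**Step 3. A test case.** Suppose a treated patient is admitted with worsening dyspnoea, survives, and the investigator thinks the tumour is the likelier cause but is not certain.

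- Under 6.3.8 the event is not unequivocally due to progression, so it is an AE. The admission makes it serious under 6.2, and 6.4 requires a report.
- Under 6.1 it may be treated as a symptom of the deteriorating disease, hence not an AE and not an SAE.
- Under 6.3.9 the admission may be treated as due to progression symptoms, hence not an SAE.

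Either site can point to the protocol's text. Section 6.3.10 does not settle the matter, because the patient did not die.

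**Step 4. Scale.** The planned enrolment is about 175 (Section 1.5), and Section 8.3.1 bases safety summaries on all treated patients. Section 8.7 also calls for presentation by the two prior-treatment cohorts, whose planned sizes follow from Section 1.5.

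- Overall: 1/175 = 0.57 percentage points per omitted patient.
- TKI-only cohort: 50 + 8 = 58; 1/58 = 1.7 points.
- TKI-plus-platinum cohort: 100 + 17 = 117; 1/117 = 0.85 points.

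The documents give no rate of equivocal events and no rate at which they are attributed to the cancer, so the total shortfall cannot be estimated from them.

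**The case against.** The best defence is that the sections can be read together. Section 6.1 is a general definition, and it gives chest pain as an example of an AE symptom. Section 6.3.8 is the dedicated text on progression, and 6.3.6 and 6.3.10 share its standard. Both 6.1 and 6.3.9 presuppose that the event is attributed to the disease, and 6.3.9 limits only SAE reporting. Section 6.3.5 requires symptoms reported by the patient or observed by staff to be recorded. Appendix A tells investigators to count ambiguous cases as possibly drug-related, and 6.3.2 asks for notification of any SAE that may be related to AZD9291. Hospital episodes and their reasons are also collected as resource-use data (Section 5.3.2.5).

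Much of this stands as mitigation. It does not remove the mismatch: the Appendix A and 6.3.2 safeguards operate only once something has been classed as an AE or SAE, and resource-use records are not AE data.

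A reader might infer two stronger things.

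- **That the protocol excludes every disease-related symptom or hospitalisation.** It does not. The exclusions are tied to deterioration of the target disease or to progression. What they lack is a threshold for uncertain attribution.
- **That signals of interstitial lung disease are hidden.** The documents do not support this. Section 6.7 brings new or worsening pulmonary symptoms to the study physician, and its work-up is meant to separate drug toxicity from alternatives such as lymphangitic carcinomatosis. None of that depends on the event first being recorded as an AE. The narrower point remains that 6.7 does not itself require an AE or SAE entry, and the AE summaries in Section 8.5 are built from recorded AEs.

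**Conclusion.** The inconsistency is real and rests on the text alone. Its consequence is a risk, not a demonstrated outcome: uneven and possibly understated AE and SAE rates for equivocal non-fatal events. Admissions are the clearest gap, because deaths have their own rule in 6.3.10. The scale figures assume that the planned numbers are treated and that the omitted patient has no other recorded event counted in the same rate. The primary endpoint, ORR by independent central review, is not affected. The point deserves correction because safety is a stated objective of an uncontrolled study and the remedy is small.

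**What to change.** Use one threshold throughout, taking the standard that the protocol already applies in 6.3.8.

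- In 6.1, limit the exclusion to deterioration and associated symptoms that are unequivocally due to disease progression.
- In 6.3.9, add the same qualifier to both sentences, the one on signs and symptoms and the one on hospitalisation.
- Move that paragraph from 6.3.9 to 6.3.8, so that the rules on progression stand in one place.

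This changes reporting text only. It costs edits to two sections, relocation of one paragraph and a reminder to sites. The downside is somewhat more AE and SAE reports, and with them slightly higher observed rates.
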